TITLE:

Effectiveness of nasal suction in infants with bronchiolitis using a NoseFrida vs. bulb syringe: a prospective observational study

NCT 04599101

Date: 10/7/2020

Study Protocol

Title: Effectiveness of nasal suction in infants with bronchiolitis using a NoseFrida vs. bulb syringe: a prospective observational study

Abstract:

Protocol version: 15-Sept-2020

Funding: The Fridababy company will supply 100 NoseFrida devices and replacement filters for use in this study. The trial design, implementation, analysis and any publication is entirely independent of the Fridababy company. The bulb syringe devices will be supplied by the Beaumont Emergency Center for those patients that will receive this device.

Background/rationale: Bronchiolitis is a common infectious process during infancy, with reported rates of up to 30% of infants affected each year [1]. The rates have been increasing in the United States and it is a common cause for hospital and PICU admission [1]. These infants also typically present with significant rhinorrhea and congestion, which poses an issue for young infants and neonates, as they are obligate nasal breathers [2]. With their increased work of breathing and the obstructing secretions, there is often, consequently, sleeping and feeding difficulties [3]. Clearing the nasal secretions and providing a patent airway is recommended to improve these symptoms [4]. One study on patients admitted to the hospital found that long intervals between suctioning led to increased length of stay [5], which may suggest that frequent suctioning is more beneficial. Despite much anecdotal experience with the NoseFrida device there is no published data comparing it to the historic standard of care, the bulb syringe. We will complete an observational cohort study with patients receiving either a NoseFrida or a bulb syringe and assess which device provides better relief to infant with bronchiolitis under 18 months of age.

Study design: The study will be an observational prospective cohort study, with one group receiving a bulb syringe and one group receiving a NoseFrida device.

Study setting: The trial will be completed at a Beaumont Children's Emergency Center with recruitment beginning as soon as IRB approved..

Inclusion criteria:

- Infants 18 months of age or younger
- Evaluated in the Emergency Center at Beaumont, Royal Oak for 6 months.
- Diagnosis of bronchiolitis, or presenting symptoms that are consistent with this diagnosis:
 - Cough
 - Difficulty in breathing
 - Wheezing
 - Decreased oral intake
 - Fever
- Initial EC visit for the current illness

Exclusion criteria:

- Clinically ill, as defined by:
 - Requiring respiratory support (ex. O2 nasal canula, or HFNC)

- Abnormal respiratory rate on most recent measurement, per PALS guidelines:
 - Infant- >53 breaths per minute
 - Toddler- >37 breaths per minute
- Any history of structural upper airway disease, including:
 - Cleft palate
 - Tracheomalacia/laryngomalacia
 - Subglottic stenosis
- Previously enrolled in the study

Intervention: Patients will be selected based on inclusion/exclusion criteria. The patient's caregiver will then be supplied with an information sheet that explains the study, and any follow-up questions will be answered. Those who verbally consent to participate will be enrolled in the study. They will then receive a device to suction their infant's nares as needed. The device supplied to each patient will be dependent on the week (we will rotate by supplying Nosefrida one week and bulb syringe the next week in order to attain similar size cohorts). Education will be given on how to use their respective suction device. Instructions on the home recording form will be supplied to the caregiver for things to monitor while using the device: the average number of times the device is used per day, number of days after discharge until respiratory symptoms resolve, until the infant is eating/drinking well, until the infant is sleeping well, in addition to the number of provider visits during 7 days after discharge. The following information will be recorded in Sharepoint: date of presentation, MRN, age, sex, cohort group, number of older siblings, prior parental use of suction devices, caregiver's email address, and phone number. Starting on day 7 after the discharge from the Emergency Center and then again day 9, a survey will be sent via RedCap. If on day 11 the survey is not completed, a phone call will be made by the investigator to confirm email and then will resend if incorrect. If correct parent will be encouraged to complete the survey, (phone script attached).

Adherence assessment: A question on the Redcap survey will verify that the caregiver used only the intended method of suctioning for the infant in the 7 days post discharge from the Emergency Center.

Outcomes:

Primary outcomes

- Number of PCP/ER/urgent care visits for the same respiratory illness within 7 days following discharge
- Hospital admission for respiratory illness or dehydration within 7 days following discharge

Secondary outcomes

- Number of days (on a scale of days 1-7) after discharge until respiratory symptoms (tachypnea, retractions, increased WOB) return to pre-illness levels
- Number of days (on a scale of days 1-7) after discharge until eating/drinking returns to pre-illness levels

- Number of days (on a scale of days 1-7) after discharge until sleeping returns to pre-illness levels
- Parental satisfaction on a likert scale (1-strongly disagree, 2-disagree, 3-undecided, 4-agree, 5-strongly agree)
 - Does this product suction babies nose well?
 - Is this product easy to use?
 - Would you recommend this product to other parents?

Sample size: At the outset of our trial design, there was no data available in the literature regarding the use of NoseFrida as a suction device. For this reason, we are not able to calculate a formal sample size that would be needed to have a specified probability of detecting a difference with our data analysis. This study will be exploratory in nature. The sample size was arbitrarily chosen at 200 participants, 100 for each cohort.

References:

1. Øymar, K., Skjerven, H. O., & Mikalsen, I. B. (2014, April 3). Acute bronchiolitis in infants, a review. Retrieved from <https://www.ncbi.nlm.nih.gov/pmc/articles/PMC4230018/>.
2. Trabalon, M., & Schaal, B. (2012). It takes a mouth to eat and a nose to breathe: abnormal oral respiration affects neonates' oral competence and systemic adaptation. Retrieved from <https://www.ncbi.nlm.nih.gov/pmc/articles/PMC3397177/>.
3. National Collaborating Centre for Women's and Children's Health (UK). (2015, June). Supportive treatment. Retrieved from <https://www.ncbi.nlm.nih.gov/books/NBK328408/>.
4. Freeman, J. F., Weng, H.-Y. C., & Sandweiss, D. (2015, January). Outpatient management of home oxygen for bronchiolitis. Retrieved from <https://www.ncbi.nlm.nih.gov/pubmed/25149905>.
5. Mussman, G. M., Parker, M. W., Statile, A., Sucharew, H., & Brady, P. W. (2013, May). Suctioning and length of stay in infants hospitalized with bronchiolitis. Retrieved from <https://www.ncbi.nlm.nih.gov/pmc/articles/PMC6291830/>.

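### The first survey is sent on day 7, inside the 7-day period it measures, so caregivers who answer that day can miss events or recovery later on day 7

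*Protocol*

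**What the plan says.** Survey timing is set in the protocol's Intervention section: "Starting on day 7 after the discharge from the Emergency Center and then again day 9, a survey will be sent via RedCap". Non-responders are then pursued: "If on day 11 the survey is not completed, a phone call will be made by the investigator to confirm email".

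The survey measures a period that includes day 7:

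- Primary outcomes: "Number of PCP/ER/urgent care visits for the same respiratory illness within 7 days following discharge" and "Hospital admission for respiratory illness or dehydration within 7 days following discharge".
- Secondary outcomes: days until respiratory symptoms, feeding and sleep return to pre-illness levels, each "on a scale of days 1-7". Day 7 is thus a scored day.
- Adherence assessment: whether the caregiver "used only the intended method of suctioning for the infant in the 7 days post discharge from the Emergency Center".
- Home recording form (Intervention): several items, "in addition to the number of provider visits during 7 days after discharge".

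The protocol gives no clock time for sending the survey, does not define day 0 or the close of the window, and does not tell caregivers to wait until day 7 is over. The SAP does not mention the date of survey completion.

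**The concern.** A survey that can be completed during the last day of its own reference period cannot record what happens after it is submitted. A visit or admission on the evening of day 7 belongs to a primary outcome but is lost if the caregiver answered that morning. Likewise, a caregiver whose infant is still unwell on the morning of day 7 cannot know whether recovery will come that day.

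Nothing described repairs this. The day 9 send and the day 11 call are aimed at completing outstanding surveys, not at updating submitted ones. The MRN is recorded, but no chart check of outcomes is described. The home form can hold a late day-7 event, but the survey has already been submitted.

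At stake is a small undercount of visits and admissions among prompt responders. If promptness differed between the devices, the two cohorts would be undercounted to different degrees.

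**Working it through.** The plan states no figure to reproduce: the sample size of 200 (100 per cohort) is declared arbitrary, and no event rate is given. The check is therefore direct arithmetic on the timing. Answer times, response shares, visit rate and half-lives below are assumptions.

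**Step 1. Window lost by one day-7 responder.** The window is 7 × 24 = 168 hours. Loss = (close of window − time of answer) / 168 h, or zero if the answer comes after the close.

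*Calendar-day reading* (window closes at midnight at the end of day 7). An answer at hour s loses 24 − s hours.

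*168-hour reading* (window closes on day 7 at the hour of discharge). With discharge hours assumed evenly spread over 24 h, the share of day-7 responders truncated is (24 − s)/24, and the mean loss over all day-7 responders is (24 − s)²/48 hours.

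| Answer on day 7 at | Calendar day: loss | 168 h: share truncated | 168 h: mean loss |
|---|---|---|---|
| 08:00 | 16 h (9.5%) | 67% | 5.3 h (3.2%) |
| 12:00 | 12 h (7.1%) | 50% | 3.0 h (1.8%) |
| 18:00 | 6 h (3.6%) | 25% | 0.75 h (0.4%) |

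The ceiling under either reading is 24/168 = 1/7 = 14.3%, for an answer at the first moment of day 7.

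**Step 2. Events lost if visits are front-loaded.** The percentages above equal the share of visits lost only if visits are spread evenly. With a visit rate that decays with half-life h, cumulative visits are proportional to F(x) = 1 − 2^(−x/h), and a full lost day misses 1 − F(6)/F(7):

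- h = 2 days: 1 − 0.875/0.9116 = 4.0%.
- h = 3 days: 1 − 0.750/0.8016 = 6.4%.

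**Step 3. Effect on the device comparison.** Let a and b be the shares answering on day 7 in the two cohorts and f the fraction of visits each such responder loses. With no true difference, the observed ratio of mean visits is (1 − a·f)/(1 − b·f). Taking the worst case, f = 1/7:

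- a = b: ratio 1.00.
- 60% vs 40%: 0.9143/0.9429 = 0.970.
- 70% vs 30%: 0.9000/0.9571 = 0.940.
- 100% vs 0% (the extreme): 0.857.

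**Step 4. Comparison with sampling error.** At an assumed mean of 0.30 visits per infant, the 60/40 case shifts the difference in means by 0.30 × (0.60 − 0.40)/7 = 0.009. With Poisson counts and 100 per cohort, the standard error of that difference is √(2 × 0.30/100) = 0.077, about nine times as large.

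**Step 5. After the change.** With the first survey on day 8, both the calendar-day window and the 168-hour window have closed before anyone can answer, so the loss is 0 h.

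**The case against.** The strongest reply is that the overlap is not certain. Seven days after discharge can mean 168 hours, and on that reading many day-7 answers arrive after the window has closed: half of those given at noon and three quarters of those given at 18:00, under the assumption in Step 1. This stands. Truncation is certain only on the calendar-day reading, and the documents do not choose between the two. It does not remove the point, because an answer before the hour of discharge is truncated on either reading.

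The survey items are also not reproduced and may already refer to the end of day 7. That is possible, but wording cannot capture an event that happens after submission.

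A reader might infer three stronger things that the documents do not support:

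- *That late responders report a longer window.* The primary outcomes, the home form's visit count and the adherence question are all fixed at 7 days, so someone answering after day 9 or day 11 is asked about the same period.
- *That 14% of events are lost.* That is the share of events falling on day 7 if they are evenly spread. Losing all of it would need every caregiver to answer at the very start of day 7.
- *That the comparison is biased.* The schedule is the same for both devices. Caregivers know which device they have, so a difference in response speed is possible, but nothing in the documents indicates one.

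**Conclusion.** The point holds as a minor one. The first survey falls within its own reference period, so some day-7 responders can miss events or recovery later that day. The loss is under 24 hours, at most 1/7 of the window, and for plausible answer times it is about 4% to 10% of the window on the calendar-day reading and 0.4% to 3% on the 168-hour reading. These figures apply only to those who answer on day 7, so the undercount across a whole cohort is smaller.

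The device comparison is affected only if response timing differs by device. Even then the effect is about 3% in the ratio at an assumed 60% versus 40% with a full day lost, well within sampling error for a study that calls itself exploratory. It would not change the interpretation of the trial, but it is avoidable at almost no cost.

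It would be wrong to blame the timing for all ambiguity at the top of the recovery scale. The 1 to 7 scale has no stated value for an infant not recovered by day 7, and that gap remains whenever the survey is sent. It should be dealt with separately.

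**What to change.** Send the first survey on day 8, the reminder on day 10, and make the call on day 12 if the survey is still incomplete. Word every item to cover the period *from discharge through the end of day 7*, which also settles when the window closes.

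The cost is a one-day shift in the REDCap schedule, a few words in the survey, and one more day of recall, which the home recording form supports.

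The SAP is dated January 2024, and the documents do not say whether data collection had finished by then. If it had, the sponsor can report survey completion dates by device, where recorded, and repeat the analysis without the day-7 responses. That repeat is a sensitivity check only, because it selects caregivers by how quickly they replied.

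### The three secondary recovery outcomes have no value for an infant already at pre-illness level at discharge, and the plan records nothing that could identify such infants later

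*Protocol*

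**What the plan says.** The Protocol (Outcomes, Secondary outcomes) defines three recovery times on the same scale:

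- breathing: "Number of days (on a scale of days 1-7) after discharge until respiratory symptoms (tachypnea, retractions, increased WOB) return to pre-illness levels"
- feeding: "Number of days (on a scale of days 1-7) after discharge until eating/drinking returns to pre-illness levels"
- sleep: "Number of days (on a scale of days 1-7) after discharge until sleeping returns to pre-illness levels"

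None has a zero or a not-affected value.

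The Inclusion criteria accept "Diagnosis of bronchiolitis, or presenting symptoms that are consistent with this diagnosis". Five symptoms are listed. Reduced oral intake is one of them; disturbed sleep is not listed. The Exclusion criteria remove infants with "Abnormal respiratory rate on most recent measurement, per PALS guidelines" and those "Requiring respiratory support (ex. O2 nasal canula, or HFNC". Retractions and increased work of breathing are not exclusions.

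The Intervention section lists what is recorded at enrolment: "date of presentation, MRN, age, sex, cohort group, number of older siblings, prior parental use of suction devices", plus contact details. Feeding, sleep and breathing status are absent. The same section describes the home form as asking for days until symptoms resolve and until the infant eats and sleeps well. It does not repeat the 1-7 limits and gives no code for an infant with no problem to begin with. The device supplied alternates by week.

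The SAP compares continuous data between arms by t-test or Mann-Whitney test, with no adjustment and no rule about who enters each comparison.

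**The concern.** A time to return to the usual level is defined only for an infant who is below that level when the clock starts. For any other infant the caregiver has no correct answer on a scale that begins at 1. Three entries are plausible: 1, 0 or nothing.

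If the entry is 1, the infant counts among the fastest recoveries in its arm, with a value that no device could have improved. In equal shares, such infants pull both arms towards 1 and hide a real difference. In unequal shares, they produce a difference that has nothing to do with the device. Weekly alternation is not randomisation and the SAP adjusts for nothing, so an imbalance cannot be ruled out. The listed data could neither reveal it nor correct it. If caregivers choose different entries, the outcome also mixes scored and missing values for the same clinical state.

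The Protocol's stated aim is to learn which device gives better relief. These three outcomes are the ones that measure symptom relief directly.

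**Working it through.** **The plan's own figure.** The Protocol sets 200 infants, 100 per cohort, and calls the number arbitrary. No alpha, power, effect or SD is given, so there is nothing to reproduce.

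**Inputs.** From the documents: 100 per arm; scale 1-7; t-test or Mann-Whitney. I take days to be handled as continuous data, which the SAP does not say. Assumed: two-sided 5%; no dropout; days among affected infants roughly normal, SD 1.8, held to 1-7; means 4.5 vs 3.7; unaffected infants scored day 1; unaffected share p varied. For scale, 100 per arm has 80% power for a standardised difference of (1.960 + 0.842) × √(2/100) = 0.396, or 0.396 × 1.8 = 0.71 day. The assumed 0.8 day is thus an effect the study could reasonably hope to detect if every infant were affected.

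**Dilution, same share p in both arms** (simulated Mann-Whitney power):

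| p | All infants, unaffected = day 1 | Affected only |
|---|---|---|
| 0% | 84% | 84% |
| 10% | 70% | 82% |
| 30% | 37% | 70% |
| 50% | 18% | 58% |

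Repeat runs, with or without rounding to whole days, agree to within about three points. With means 4.0 vs 3.2 the pattern is the same: 85% at p = 0; 72% vs 81% at 10%; 41% vs 71% at 30%; 21% vs 56% at 50%.

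**Check by formula** (means 4.0 vs 3.2, normal approximation). Difference = 0.8(1 − p). Mixture SD = √[(1 − p) × 1.8² + p(1 − p) × (4.0 − 1)²]. At p = 0.3:

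- difference = 0.8 × 0.7 = 0.56
- SD = √(0.7 × 3.24 + 0.21 × 9) = √4.158 = 2.04
- z = 0.56 / (2.04 × √(2/100)) − 1.96 = −0.02, so power is about 49%
- affected only, 70 per arm: z = 0.8 / (1.8 × √(2/70)) − 1.96 = 0.67, so power is about 75%

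At p = 0 the formula gives 88%. A t-test therefore loses somewhat less than the Mann-Whitney test, but in the same direction.

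**Imbalance, no device effect.** The spurious mean difference is (p₂ − p₁) × (mean among affected − 1). With a mean of 4.0 and a 10-point gap it is 0.10 × 3.0 = 0.30 day. Simulated rejection at the 5% level is about 5% with equal shares (30% and 30%), about 9% at 30% vs 35%, and about 21% at 30% vs 40%. A comparison of affected infants only stays near 5% throughout.

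**The case against.** Several stronger readings are tempting, and the documents do not support them.

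- **That many enrolled infants are unaffected.** The criteria permit such infants but give no proportion. The Protocol's background points the other way for two domains: "there is often, consequently, sleeping and feeding difficulties".
- **That these infants will be scored day 1.** Day 1 is the lowest value on the scale and a likely answer, but the home form as described would allow a 0, and a blank is possible. The survey items are not in the documents. A blank would make the value missing instead of diluting the comparison.
- **That entry empties the respiratory outcome.** The rate limits remove marked tachypnea only. Retractions and increased work of breathing remain, difficulty in breathing and wheezing are entry symptoms, and an infant under the limit may still breathe faster than its own usual rate. Sleep is the clearest case.
- **That the scale by itself creates a false device effect.** It does so only if the unaffected share differs between arms. No passage indicates a gap of any given size, and alternating weeks keep the calendar periods similar.
- **That unaffected infants carry no information.** An infant who is well in one domain at discharge can worsen at home, and simply dropping such infants would lose that.

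The cost at small shares is also modest: at 5% unaffected, all-infant power is still about 79%. Restricting to affected infants does not restore the full 84% either, because fewer infants remain. Finally, these are secondary outcomes of a study that calls itself exploratory, so no stated power target is missed.

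All of this stands. None of it supplies the missing code, the missing status at discharge or the missing analysis rule.

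**Conclusion.** The concern holds as a gap in outcome definition and data collection. Infants already at their pre-illness level at discharge are eligible, have no defined score, and could not be separated afterwards from the data listed. Their share is unknown. If they are scored day 1, power for a 0.8-day difference falls from about 84% to about 70%, 37% and 18% at shares of 10%, 30% and 50%. An affected-only comparison would keep 82%, 70% and 58%. A false difference is conditional on imbalance: about 9% rejections for a 5-point gap and 21% for a 10-point gap. The effect, SD and shares are assumptions; the direction does not depend on them, but the size does. The change is worth making because it is cheap and concerns the outcomes closest to the study's aim. Return visits and admissions, the primary outcomes, are unaffected.

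**What to change.** 1. At enrolment, before any use of the device, ask the caregiver three yes/no questions: are breathing effort, feeding and sleep each currently worse than before this illness? Record the answers with the other baseline data.
2. Add a separate response, not affected at discharge, to each recovery item on the home form and in the survey, kept apart from day 1 and from a blank.
3. In the SAP, compare days to recovery in each domain among infants recorded at enrolment as affected in that domain. Use the enrolment answer, not the later survey recall, to define the group. Report the number not affected per arm, report separately any infants unaffected at discharge who later worsened, and keep the all-infant comparison as a sensitivity analysis.

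If data collection is already complete, state in the SAP how day 1, 0 and blank answers are handled and report their counts per arm.

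The cost is three questions, one response option per item and a short SAP paragraph; clinical care does not change. The downside is a smaller denominator for each recovery outcome. The change removes the effect of unequal unaffected shares but not other confounding from week-by-week allocation.
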